4.3 Justification for Dose

Tip: RFT3, 15mJ 50Hz 0.75W 0% air 0% water, following the manufacturer instructions (*attachment 3*).

4.4 End of Study Definition

A participant is considered to have completed the study if he or she has completed all phases of the study including the last visit or the last scheduled procedure shown in the Schedule of Activities (SoA), Appendix Section 12.1.

5 STUDY POPULATION

5.1 Inclusion Criteria

In order to be eligible to participate in this study, an individual must meet all of the following criteria:

1. Provision of signed and dated informed consent form.
2. Stated willingness to comply with all study procedures and availability for the duration of the study.
3. Male or female (Gender is not an inclusion or exclusion criteria), aged 18 years old or above.
4. In good general health as evidenced by medical history or non-contributory medical history (Patient can be seen for regular dental appointment in PDM; ASA classes I and II).
5. Radiographic presence of periapical radiolucency.
6. Negative response to thermal sensitivity testing (difluorodichlormethane at -50 °C, Endo-Ice, Coltène/Whaledent Inc., Cuyahoga Falls, Ohio) or electric pulp testing.
7. Enough tooth structure for adequate isolation with rubber dam.
8. No history of previous endodontic treatment on the tooth.
9. Teeth with single canal and lower molars with two mesial canals.

5.2 Exclusion Criteria

Economic status, gender, race or ethnicity are not of concern for the proposed investigation and therefore for study exclusion. The cut-off age of 18 years was only chosen so as to limit the need for parental consent. Patients will not be eligible to participate in the study if any of the following exclusion criteria applies:

1. Patients who report they are pregnant.
2. Teeth affected by dental trauma.
3. Periodontal changes (pockets 3 mm, mobility I or gingival edema).
4. Radiographic presence of resorptive processes.
5. Per the investigator's discretion, unable or unlikely to comply with study procedure.
6. Presence of any condition which, in the opinion of the investigator, makes participation in the study not in the individual's best interest.

5.3 Lifestyle Considerations

N/A

5.4 Screen Failures

Screen failures are defined as participants who consent to participate in the clinical trial but are not subsequently randomly assigned to the study intervention or entered in the study. A minimal set of screen failure information is required to ensure transparent reporting of screen failure participants, to meet the Consolidated Standards of Reporting Trials (CONSORT) publishing

requirements and to respond to queries from regulatory authorities. Minimal information includes demography, screen failure details, eligibility criteria, and any serious adverse event (SAE).

Individuals who do not meet the criteria for participation in this trial (screen failure) may be rescreened. Rescreened participants should be assigned the same participant number as for the initial screening.

5.5 Strategies for Recruitment and Retention

Patients may be prescreened (through medical records/phone script) and will be contacted and informed about the study ahead of time, at least 1 day before their appointment. We will try our best to contact patients and inform them about the study ahead of time, but sometimes it may not be possible. The Endodontics clinic is a referral based clinic, sometimes we see new external referrals or emergency patients. We don't have any direct contact with those patient ahead of time, and sometimes emergency patients would show up without prior appointments. Thus, patient may be included even if they haven't been contacted prior.

Patients presenting to the Department of Endodontics, School of Dental Medicine (PDM), University of Pennsylvania for evaluation and routine endodontic treatment of infected, necrotic teeth with chronic apical periodontitis will be asked to take part in the study if they appear to meet the inclusion criteria specified above. Patients will be asked if they were interested to participate in this investigation after a clinical diagnosis matching is confirmed and the patient/tooth meets the inclusion criteria specified above. Initial clinical diagnosis will be made by a postgraduate resident and verified by the supervising faculty. The PI, a full-time faculty, and the co-investigator, endodontic resident, will be informed about a potential study participant, verify the diagnosis and ask for participation (including consent and alternatives). Any recruitment materials that are developed will be submitted to the IRB for approval prior to use. No non-registered PDM patients will be asked to participate in the study.

6 STUDY INTERVENTION

6.1 Study Intervention(s) Administration

6.1.1 *Study Intervention Description (attachment 3)*

- **Dimensions:**

- Laser console (W x L x H) 9 x 18 x 12 in (23 x 46 x 30.5 cm)
- Tablet (W x H x D) 6.7 in x 9.3 in x 0.2 in (16.9 cm x 23.8 cm x 0.6 cm)
- Screen size 9.7 in (24.6 cm)
- Weight laser console (with water) 27.2 lbs (12.3 kg)
- Weight Tablet 0.9 lbs (390 g)

- **Electrical:**

Class I Medical Electrical (ME) Equipment

- Operating voltage 100 - 240 VAC
- Frequency 50 / 60 Hz
- Current rating 6A / 3A
- Main control Main Power Switch
- On / Off control Keyswitch
- Remote interruption Remote interlock connector

- **Air and water spray:**

- Water type Distilled or De-Ionized only
- External air source 60-120 psi. (4.1 – 8.2 bar)
- Water 0 - 100%
- Air 0 - 100%

- **Optical:**

- Laser classification IV (4)
- Medium Er,Cr:YSGG (Erbium, Chromium: Yttrium, Scandium, Gallium, Garnet)
- Wavelength 2.78 µm (2780nm)
- Mode Free-running Pulsed
- Frequency (Pulse Rate) 5 – 50 Hz
- Average power 0.1- 4.0 W
- Power accuracy \pm 20%
- Pulse energy 10– 250 mJ
- Pulse duration for “H” mode (Short pulse) 60 µs
- Pulse duration “S” mode (Long pulse) 700 µs
- Handpiece head angles 70° contra-angle
- Fiber Tip diameter range (Spot size) 200 – 1200 µm
- Output divergence \geq 8° per side
- Aiming beam 625-670 nm (red) laser, 1mW max (Laser Class 1)
- Nominal ocular hazard distance (NOHD) 5cm
- Maximum permissible exposure (MPE) $3.46 \times 10^5 \text{W/m}^2$

6.1.2 Dosing and Administration

For standard irrigation protocol group (NaOCl group): canals will be instrumented up to size 30/0.04 taper using 1.5cc of 3% NaOCl in between files following the standard endodontic procedure protocol.

For Er,Cr:YSGG laser group: canals will be instrumented up to size 30/0.04 taper using 1.5cc of normal saline in between files, then rinse each canal with 1cc normal saline and flood the access. Then ER:Cr;YSSG laser 2780nm (Waterlase Express™, BIOLASE®) with 300µm tip (EdgePro #3, RFT 3) will be placed into the mid-root of the canal. The tip will be activated and slowly withdrawn to the orifice (1-2mm/sec) following the manufacturer settings (energy 15mJ, repetition rate 50Hz, 0% air, 0% water).

When the final 30.04 taper apical size is reached. All canals in all groups will be irrigated with 5cc of 3% NaOCl with the ultrasonic irrigant activation following the standard endodontic procedure protocol.

6.2 Preparation/Handling/Storage/Accountability

6.2.1 Acquisition and accountability

The study intervention and control products (both drugs and devices) are regularly available and routinely used in the Endodontic clinic, and will be provided to the investigator as needed.

6.2.2 Formulation, Appearance, Packaging, and Labeling

N/A

6.2.3 Product Storage and Stability

Control (NaOCl): Will be stored and used as regulated by the Endodontic clinic.

Waterlase Express™ and accessories will be stored in a cool dry place when not in use. Storage temperature should be 5° to 45°C (41°F to 113°F), relative humidity 10% to 90%, non-condensing. Cover the system when not in use for extended periods of time and store in a place where it will not be accidentally bumped or banged.

6.2.4 Preparation

Control (NaOCl): 12cc syringe will be filled with 3% NaOCl to be dispensed using 30 gauge needle as used routinely in the Endodontic clinic.

Waterlase Express™:

- Daily start-up:

- Power up the Tablet. Verify that all connections have been properly secured; turn the main power switch at the back of the console ON (I) (when the power switch is OFF, LEDs will not light up); insert the key into the Keyswitch and rotate it clockwise to the ON (I) position. The LED light on

the Tablet Holder lights up when the Tablet is properly powered on and docked in the Tablet Holder, connected and active.

- Make sure the air supply is connected and verify that the patient water bottle is no less than $\frac{1}{3}$ full with distilled or de-ionized water. It is suggested to completely fill the patient water bottle at the start of the day.

- Initiating the Laser From off Status:

- Turn the main power switch at the back of the console ON (I) (when the power switch is OFF, LEDs will not light up); insert the key into the Keypad and rotate it clockwise to the ON (I) position
- Press and hold the power switch on the right side of the Tablet to turn it on
- The startup screen will appear, and the system software will begin to load (approximately 30 seconds)
- Verify that the Footswitch and laser are paired
- Attach the Handpiece to the Fiber Optic Cable
- Ensure the tablet is properly docked in the Tablet Holder and secured with the Tablet Latch.
- All users configured to the system listed on the User selection screen; select the proper account. A screen will appear giving the user the option to prime the Handpiece or skip this step (if the Handpiece is already primed). If "prime" is chosen, a message will appear confirming that priming is taking place (approximately 6 seconds).

After priming, set-up is complete; the system will now transition to the home (Procedure) screen in Standby mode.

- Activating the Waterlase Express™:

Place the system into Ready mode after selecting a procedure (Endodontic) by pressing the Function Control Button on the Tablet Holder; wait approximately 2 seconds, then press down on the Footswitch when ready to fire the laser.

6.3 Measures to Minimize Bias: Randomization and Blinding

Simple randomization by generating simple allocation sequence, allocation concealment, and implementation of the random allocation sequence upon enrollment.

As this is part of a procedure, the investigator and study participant cannot be blinded to the treatment. To minimize bias, the investigator will provide the same information regarding reporting pain to all study participants.

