9.2 Sample Size Determination

Decrease in microbial load based in CFU.

Sample size calculation, with 80% power ($\beta = 0.20$), indicated a minimum sample size of 52 teeth (26 per group) to show a 5% ($\alpha = 0.05$) difference between groups. The calculations were made in the G*Power 3.1 program.

Test: Independent t test.

Two tails.

Statistical test: Means: Wilcoxon-Mann-Whitney test (two groups).

Effect size: 0.8 (large)

$\alpha = 0.05$, $\beta = 0.20$

Attrition rate of 30% was considered, indicated a minimum sample size of 76 teeth (38 per group).

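### Simple randomisation leaves the balance of tooth type to chance, and neither the primary analysis nor the named baseline variables account for it

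*Combined protocol and SAP*

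**What the plan says.** All references are to the combined protocol and SAP.

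- **Allocation.** Section 6.3 describes the method as "Simple randomization by generating simple allocation sequence, allocation concealment, and implementation of the random allocation sequence upon enrollment". It names no blocks, strata or minimisation, and it says that neither investigator nor participant can be blinded.
- **Eligible teeth.** Section 5.1 admits "Teeth with single canal and lower molars with two mesial canals". Section 4.1 samples the canals targeted for treatment.
- **Size.** Section 9.2 arrives at "indicated a minimum sample size of 52 teeth (26 per group") and, after allowing for 30% attrition, a "minimum sample size of 76 teeth (38 per group").
- **Primary analysis.** Section 9.4.2 names Friedman's and Wilcoxon signed-rank tests. Sections 4.1 and 8.1 name the independent t test and the Wilcoxon-Mann-Whitney test. None is specified with a covariate or stratum.
- **Baseline and subgroups.** Section 9.4.5 names age, gender, preoperative pain and endodontic diagnosis. Section 9.4.7 marks subgroup analysis as not applicable. Tooth number is collected (2.3.1), so tooth type will be known.

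**The concern.** The protocol itself suggests why tooth type could matter for the primary endpoint. Section 2.2 says that biofilm often survives in anatomical complexities such as isthmuses and accessory canals, and attributes persistent infection partly to them. The number of canals sampled may also differ between the two kinds of tooth.

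If tooth type affects CFU reduction, a chance difference in molar share moves the unadjusted treatment difference, and the spread between tooth types adds to the error variance. Nothing in the plan removes either effect. Because tooth type is not among the named baseline variables, a reader of the results might not see an imbalance at all. At stake are precision and the credibility of the comparison in a small open trial, not the validity of the randomisation.

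**Working it through.** **Inputs.** From 9.2: standardised effect 0.8, two-sided alpha 0.05, 80% power, 26 per group before and 38 per group after attrition. Allocation probability 0.5 is implied by the equal groups. The molar share is not in the documents; 30-50% is assumed, with 20% as a lower check.

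**1. The plan's own figure.** For a t test the noncentrality is d × √(n1·n2/(n1+n2)). At 26/26 this is 0.8 × √13 = 2.88 on 50 degrees of freedom, giving 80.7% power. Inflating, 26/0.7 = 37.1, rounded up to 38 per group, 76 in all. The figure reproduces.

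**2. Arm sizes.** One arm's size is Binomial(76, 0.5), with SD √76/2 = 4.4. An exact 38/38 split has probability 9.1%, and a split of 32/44 or worse 20.7%. The effect on power is small:

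| Evaluable | Split | Noncentrality | Power |
|---|---|---|---|
| 76 | 38/38 | 0.8 × √19 = 3.49 | 93.1% |
| 76 | 32/44 | 0.8 × √18.53 = 3.44 | 92.5% |
| 76 | average over simple randomisation | | 92.8% |
| 52 | 26/26 | 2.88 | 80.7% |
| 52 | average over simple randomisation | | 80.0% |

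The average loss is 0.3 points at 76 and 0.8 points at 52.

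**3. Tooth type.** With M molars among 76 teeth, let a ~ Binomial(M, 0.5) be the molars and c ~ Binomial(76 − M, 0.5) the other teeth in one arm. The gap in molar share is |a/(a+c) − (M−a)/(76−a−c)|. As a rough check, its SD is about √(p(1−p) × 2/38), which is 0.105 at p = 0.3 and 0.115 at p = 0.5. A 15-point gap is then 1.43 or 1.31 SDs, with two-sided probability 15% or 19%. Exact enumeration gives:

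| Assumed molar share | Gap of 15 points or more, M fixed | Same, M random |
|---|---|---|
| 20% (M = 15) | 10.9% | 10.3% |
| 30% (M = 23) | 15.8% | 15.7% |
| 50% (M = 38) | 20.7% | 20.0% |

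The median gap is 7 to 8 points at 30-50% molars.

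**4. Equal arms alone do not help.** Forcing 38/38 without stratifying still gives a gap of 15 points or more in 13% of trials at 30% molars and 25% at 50%.

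**5. What an imbalance would do.** Suppose tooth type shifts the outcome by g within-type SDs (assumed 0.5 to 1). A 15-point gap moves the unadjusted difference by 0.15g, that is 0.075 to 0.15 SD, or 9% to 19% of the planned 0.8. Ignoring tooth type also inflates the variance by 1 + g²p(1−p). At g = 1 and p = 0.5 this is 1.25, and the effective effect size falls to 0.8/√1.25 = 0.72.

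**6. What adjustment buys.** Trials were simulated under simple randomisation with 30% or 50% molars and normal outcomes, and analysed by a linear model with and without tooth type. The change in power from adjusting, in percentage points, was:

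| Shift by tooth type | 52 evaluable | 76 evaluable |
|---|---|---|
| none | about −1 | less than −0.5 |
| 0.5 SD | about +1 to +2 | about +1 |
| 1 SD | about +7 to +9 | about +5 to +6 |

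**The case against.** Simple randomisation is a legitimate method. It gives an unbiased comparison, and chance imbalance is already allowed for in the test's error rate. The endpoint is a reduction from a pre-treatment sample, which removes at least part of any difference in starting load, so tooth type must influence the reduction itself to matter. The documents quantify neither that influence nor the molar share. All of this stands. It limits the point to precision and comparability, and it makes the harm conditional.

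Three stronger readings are tempting, and the documents do not support them.

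- A reader might infer that the sample size fails because 38/38 is unlikely. Section 9.2 gives a planning minimum, and step 2 shows that the cost is under 1 point of power on average.
- A reader might infer that uneven allocation combined with 30% attrition will leave an arm below 26 for the primary comparison. All CFU samples are taken at Visit 1 (visit table in 1.2; schedule in 12.1), so later missed visits cannot remove them, and participants randomised but not treated may be replaced (7.2). Without that attrition, the chance that either arm has fewer than 26 is 0.4%. Some samples may be lost or unusable, but nothing suggests 30%.
- A reader might infer that tooth type will be unbalanced. It is left to chance; a large gap is a minority outcome.

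Nor is blocking free of cost. In a simulation of blocks of 2, 4 and 6 within two strata (40% molars assumed), exactly 38/38 occurred in about 57% of trials. An unblinded person guessing the lagging arm was right about 70% of the time, against 50% under simple randomisation.

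**Conclusion.** The point holds as a gap in design and analysis taken together: tooth type is neither balanced by allocation, nor adjusted for, nor named for reporting at baseline. At an assumed 30-50% molars, about 16-20% of trials would show a gap in molar share of 15 points or more; at 20% molars, about 10-11%. Any effect on the primary comparison depends on tooth type influencing CFU reduction, which section 2.2 makes plausible but does not quantify. The randomisation is valid and the sample size is not undermined. This is a worthwhile, inexpensive improvement and not a defect that invalidates the trial.

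**What to change.** **Main change.** In 9.4.2, state a between-group comparison of CFU reduction that is adjusted for or stratified by tooth type. Two options are a linear model on log CFU reduction with treatment and tooth type as factors, or a stratified (van Elteren) Wilcoxon-Mann-Whitney test. The log model needs a rule, set in advance, for zero counts. In 9.4.5, add tooth type by arm to the baseline table. In 9.2, describe 38 per group as a target.

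**Cost.** No new data are needed, since tooth type is established at eligibility and tooth number is recorded. The primary analysis text must be rewritten, because the tests it now names take no covariate. If tooth type proves irrelevant, adjustment costs about 1 point of power or less.

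**Optional.** If the allocation list can still be changed, stratify it by tooth type using randomly varying blocks that exclude size 2, held where treating staff cannot see it; REDCap is already in use. The cost is a new list and some predictability, because the investigator is unblinded. If the list is fixed, the analysis change can stand alone.

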4 STUDY PLAN

4.1 Study Design

All the steps and procedures described are part of the standard of care root canal procedure except for sampling and the addition of Waterlase Express™ laser which are specific study procedures. All study specific procedures are **in bold** in this section.

The patient will be anesthetized, and the tooth isolated with rubber dam. Chlorhexidine 2% will be used to disinfect the tooth and the rubber dam. The removal of caries and the endodontic access will be carried out by sterile high-speed carbide burs. **Chlorhexidine 2% will be used to disinfect the tooth and the rubber dam one more time and bacteriological sample (S0) will be taken from the tooth surface.** After initial access to the root canal orifices, **a bacteriological sample will be taken from the targeted canals (S1). Sterile paper points will be placed into the canal orifices, allowed to saturate and then transferred to a vial containing reduced transport fluid (RTF).**

For NaOCl group, canals will be instrumented up to size 30/0.04 taper using 1.5cc of 3% NaOCl in between files. **For Er,Cr:YSGG laser group, canals will be instrumented up to size 30/0.04 taper using 1.5cc of normal saline in between files, then rinse each canal with 1cc normal saline and flood the access. Then ER:Cr;YSSG laser 2780nm (Waterlase Express™, BIOLASE®) with 300µm tip (EdgePro #3, RFT 3) will be placed into the mid-root of the canal. The tip will be activated and slowly withdrawn to the orifice (1-2mm/sec) following the manufacturer settings (energy 15mJ, repetition rate 50Hz, 0% air, 0% water). When the final 30.04 taper apical size is reached, a second bacterial sample will be taken (S2).**

Standard root canal procedures:

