7.2 Participant Discontinuation/Withdrawal from the Study

Participants are free to withdraw from participation in the study at any time upon request.

An investigator may discontinue or withdraw a participant from the study for the following reasons:

- Significant non-compliance to attend scheduled visits
- If any clinical adverse event (AE), laboratory abnormality, or other medical condition or situation occurs such that continued participation in the study would not be in the best interest of the participant
- Disease progression which requires discontinuation of the study
- If the participant meets an exclusion criterion (either newly developed or not previously recognized) that precludes further study participation

The reason for participant discontinuation or withdrawal from the study will be recorded on the Case Report Form (CRF). Subjects who sign the informed consent form and are randomized but do not receive the treatment may be replaced. Subjects who sign the informed consent form and are randomized and receive the treatment, and subsequently withdraw, or are withdrawn or discontinued from the study, will not be replaced.

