12 APPENDIX

12.1 Schedule of Activities (SoA)

Procedures	Pre-Screening Up to Day 0	Enrollment/Baseline Visit 1, Day 0	Study Visit 2 Day 7 +/-3 days	Study Visit 3 6 months +/-7 days	Study Visit 4 1 year +/-7 days	Study Visit 5 2 years +/-7 days
Prescreening (medical records, phone script)	X					
Study informed consent		X				
Demographics		X				
Medical history review/update		X	X	X	X	X
Clinical assessment		X	X	X	X	X
Vital signs (Blood pressure)		X	X	X	X	X
Randomization		X				
Administer study intervention		X				
Sample collection		X				
Pain Assessments (pre-op, and 4, 24, and 48 hours post-op)		X				
Adverse event review and evaluation		X	X	X	X	X
Radiologic/Imaging assessment		X	X	X	X	X
Completion of the study						X

END OF DOCUMENT

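### The arm is assigned on enrolment and nothing withholds it until the baseline sample S1 is taken, so half of the primary CFU reduction can be collected with the arm known, for no procedural reason

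*Combined protocol and SAP*

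**What the plan says.** **Allocation and blinding.** Section 6.3 (Measures to Minimize Bias) specifies "Simple randomization by generating simple allocation sequence, allocation concealment" and "implementation of the random allocation sequence upon enrollment". It adds that "the investigator and study participant cannot be blinded to the treatment". No concealment mechanism is described, and no moment is given at which the operator learns the arm.

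**Order of events.** The Schedule of Activities (12.1) puts consent, randomisation, intervention and sampling in one column, "Enrollment/Baseline Visit 1, Day 0", without an order inside the visit. Section 4.1 gives the clinical order: rubber dam, disinfection, caries removal and access, second disinfection and S0. Then "a bacteriological sample will be taken from the targeted canals (S1"). Only after S1 do the arms separate, with NaOCl between files in one, and saline followed by the laser in the other.

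**Labels.** Sections 4.1 and 8.1 have each vial, S0 and S1 included, labelled with tooth number, sample number and experimental group.

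**Eligibility.** Under 5.5 the patient is invited once the diagnosis is confirmed and the inclusion criteria are met. Under 5.4 a screen failure is someone who consented but was not randomised or entered. Criterion 9 of 5.1 is "Teeth with single canal and lower molars with two mesial canals".

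**Withdrawal, replacement and analysis set.** Section 7.2 lists as a ground for withdrawal "If the participant meets an exclusion criterion (either newly developed or not previously recognized) that precludes further study participation", and says that patients "randomized but do not receive the treatment may be replaced". Section 9.3 describes the analysis population as patients who meet the inclusion criteria, not as all those randomised.

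**The concern.** The primary endpoint (9.1, 9.4.2) compares CFU reduction between arms, so every value needs a baseline count. S1 is taken by hand. Sections 4.1 and 8.1 say that paper points are placed in the orifices and left to saturate, but give no number of points, depth or dwell time. An operator who knows the arm could sample differently at baseline without departing from the protocol. A higher S1 in one arm looks like a larger reduction in that arm.

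The second route is narrower. Between enrolment and the start of arm-specific treatment, the opened tooth may prove not to have the canal configuration that was expected. The patient is then randomised but untreated, and whether to keep or replace that patient can be decided with the arm known. Section 9.3 as worded would also let such a tooth drop out of the analysis.

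Both routes arise from timing alone. The only bias measure in 6.3 beyond randomisation and concealment concerns how patients are told to report pain, not the CFU endpoint.

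**Working it through.** **1. The plan's own sample size.** Inputs from 9.2: effect size 0.8, two-sided alpha 0.05, power 80%, two equal groups, 30% attrition. The exact t-test calculation gives 25.52, so 26 per group (power 0.807). For attrition, 26 / (1 − 0.30) = 37.1, so 38 per group and 76 in all. The stated 26 and 38 per group reproduce. Timing of allocation enters none of these inputs.

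**2. Is the arm available before S1?**

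| Step | Section | Arms differ? |
|---|---|---|
| Allocation on enrolment | 6.3 | – |
| Rubber dam, caries removal, access, S0 | 4.1 | No |
| S1 | 4.1, 8.1 | No |
| Instrumentation with NaOCl, or saline then laser | 4.1, 6.1.2 | Yes |
| S2, then common NaOCl with ultrasonic activation, then S3 | 4.1 | – |

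Allocation is placed at the top of this sequence and no step delays its disclosure. The arm on the S0 and S1 labels points the same way. No step up to and including S1 needs the arm.

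**3. What a shift in S1 would do (illustration only).** The documents give no estimate of such a shift, so its size is assumed. If knowledge of the arm moves mean S1 in one arm by s standard deviations of the reduction, and the later sample is unaffected, the mean reduction moves by s. With no true difference, the two-sided 5% t test with n per group has noncentrality s × √(n/2) on 2n − 2 degrees of freedom. The false-positive rate is the probability that |t| exceeds the 5% critical value.

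| Assumed s | n = 38: s × √19 | False positive | n = 26: s × √13 | False positive |
|---|---|---|---|---|
| 0.1 | 0.436 | 7.1% | 0.361 | 6.4% |
| 0.2 | 0.872 | 13.8% | 0.721 | 10.9% |
| 0.3 | 1.308 | 25.2% | 1.082 | 18.6% |

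Against the planned effect of 0.8, these shifts are 0.1/0.8 = 12.5%, 0.2/0.8 = 25% and 0.3/0.8 = 37.5%.

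**4. Late ineligibility.** The documents give no rate at which access overturns an entry criterion. For scale only, an assumed 5% of 76 teeth is 3.8, or about 4 teeth.

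**The case against.** **Eligibility.** A reader might infer that an unblinded operator settles eligibility once the tooth is open. The documents do not support that. Sections 5.4 and 5.5 put eligibility before randomisation, with the diagnosis verified by faculty and again by the investigators. Necrosis is established by a negative thermal or electric test (criterion 6), not by inspection of the opened tooth. Adequate structure for isolation (criterion 7) is first tested when the rubber dam goes on, which precedes caries removal and access. The withdrawal clause in 7.2 speaks of exclusion criteria, whereas canal configuration is an inclusion criterion. None of the specific exclusions in 5.2 is a finding on access, and only its two discretionary items could reach one. Nor do the documents say that the person treating is always the investigator who decides on withdrawal. This objection largely stands. What remains is canal configuration revised on access, combined with the replacement sentence.

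**Knowledge of the arm at S1.** No sentence says that the operator knows the arm at S1. Section 6.3 names concealment, and the rows of the SoA are not chronological: intervention is listed above sampling. That is fair. It is a strong inference from 6.3 and the vial labels, not a stated fact. The plan still contains nothing that would prevent it.

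**Size.** A reader might take 7% to 25% as the expected false-positive rate. It is not. Those figures require a consistent shift in one direction, of assumed size. Transport volume, dilutions and inoculum are fixed, which limits discretion after collection, though not during it.

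**Limited reach.** The operator must know the arm by S2, so deferral protects only the baseline. That is correct, and it is why this is not a critical flaw.

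**Conclusion.** The point holds for S1, and in a residual form for late ineligibility. As written, the baseline half of the primary endpoint can be collected and labelled with the arm known, although neither treatment nor sampling requires it. A patient found unsuitable on access can also be replaced after randomisation with the arm known. The change should be made because it costs little, not because bias has been shown.

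The direction and size of any bias are unknown. The illustrative rates at 38 per group (about 7%, 14% and 25%) rest on assumed shifts of 0.1, 0.2 and 0.3 SD. They also assume equal arms, a t test as in 9.2, and a reduction taken as S1 minus a later sample. Section 9.4.2 gives neither that formula nor the later time point. The sample size of 26 evaluable and 38 enrolled per group is unaffected.

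**What to change.** 1. **Section 6.3 and SoA.** Replace "implementation of the random allocation sequence upon enrollment" with: *the concealed allocation is opened at Visit 1 only after access, a check that the existing 5.1 and 5.2 criteria still hold, and collection and sealing of S0 and S1.* State that opening is the moment of randomisation, and order the Visit 1 rows of the SoA to match.
2. **Section 5.4.** A tooth that fails an existing criterion before that point is a screen failure and receives routine care. Add no new eligibility criterion. In particular, do not add a requirement to confirm necrosis in the opened tooth.
3. **Sections 4.1 and 8.1.** Label S0 to S3 with a study code and sample number, without the arm. Section 10.1.3 already provides a unique study number. This also keeps the arm off the vials from which colonies are counted.
4. **Sections 7.2 and 9.3.** Delete replacement of randomised patients. Define the primary analysis set as all randomised teeth with samples, analysed as randomised.

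**Cost.** These are text changes in a few sections and a new label format, with no extra visits, staff or patients. The small downside is opening the allocation mid-procedure with the laser ready for every case. Section 6.2.4 describes a standby mode and about 30 seconds of software loading. Losses no longer replaced fall within the 30% attrition allowance (76 × 0.30 = 22.8 teeth). Collection of S2 and S3 remains unblinded.
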